#### *Dose regimen groups*

Dose regimen groups in the extension term after Week 24 will be defined as follows:

- 300 mg q2w group: participants who were administered at least 1 dose of the 300 mg q2w regimen and never experienced q4w administration during the extension term after Week 24
- 300 mg q4w group: participants with stable disease who were administered at least 1 dose of the 300 mg q4w regimen during the extension term after Week 24

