- a Past medical history, including allergic comorbidities (asthma, aspirin sensitivity, allergic rhinitis, etc.). Surgeries for NP, including number, type and dates of sinonasal surgeries, and polypectomies, in the past will be recorded. Systemic corticosteroid use (number of courses, doses, route of administration, and duration) in the past 2 years before V1 and/or contraindication/intolerance to SCS, as well as long-term antibiotics use (>2 weeks) in the previous year, will be entered in the e-CRF. NERD will be assessed through a specific questionnaire (Appendix 11 [Section 10.11]).
- b Call IVRS/IWRS to register visit and obtain next IMP kit numbers assignment or report potential definitive IMP stop.
- c Investigational medicinal product will be administered q2w (after Week 24, some participants can be administered q4w). Between visits, at site or home administration is allowed after the second dose. Investigational medicinal product will be administered after the completion of all scheduled clinical assessments at the visit or at home. The planned last dose is at Week 48 or 50. For participants who have stable disease at Week 24, the dosing interval can be changed from q2w to q4w at the discretion of the Investigator; the reason for the change in dosing regimen should be recorded in the e-CRF. Other participants will receive the q2w regimen until Week 50. Stable disease is defined as NPS improvement from baseline to both Weeks 16 and 24 of ≥ 2 points.
- d Nasal endoscopy: endoscopy (including use of decongestants before the procedure) will be performed after all other efficacy assessments have been completed for each visit. Standard video sequences will be downloaded by the Investigator to the central reader's secured internet site. For eligibility, central reading of V1 will be used. At V2, the Investigator will review the V1 results from the central reader to confirm entry criteria and reconfirm eligibility based on a review of the inclusion/exclusion criteria and the V2 endoscopy local reading. To confirm eligibility at V2, only the V1 central reading will be made available to the site. In addition, at V2, the Investigator will perform the NE to confirm eligibility score and enter the result in the e-CRF. Thus, the participant will be considered eligible based on a V1 central reading followed by a V2 local reading NPS score of 5 or more and at least 2 on each side.
- e Computerized tomography scan to be done during the Screening Period.

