6.5 DOSE MODIFICATION

For participants who have stable disease (NPS improvement from baseline to both Weeks 16 and 24 is ≥ 2 points), the dosing interval can be changed from q2w to q4w at the discretion of the Investigator at Week 24. Participants who proceed to the dosing interval from q2w to q4w will not be permitted to return to the q2w regimen during this study. The maximum dose will not exceed dupilumab 300 mg q2w.

However, any dose reduction is not allowed other than above.

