8.1.1 Nasal endoscopy: nasal polyp score

The NPS ([4](#), [5](#), [6](#)) is assessed by central video recordings of NE. The NPS is the sum of the right and left nostril scores, as evaluated by means of NE. Nasal polyp is graded based on polyp size described in [Table 3](#).

Table 3 - Endoscopic nasal polyp score

Polyp Score	Polyp Size
0	No polyps
1	Small polyps in the middle meatus not reaching below the inferior border of the middle turbinate
2	Polyps reaching below the lower border of the middle turbinate
3	Large polyps reaching the lower border of the inferior turbinate or polyps medial to the middle turbinate
4	Large polyps causing complete obstruction of the inferior nasal cavity

Nasal endoscopy should be performed at the end of the scheduled visits before the administration of IMP and should be preceded by local administration of anesthetic drugs in combination with a decongestant.

Standard video sequences will be downloaded or sent to a centralized reader. Centralized imaging data assessments and scoring by independent physician reviewer(s) for the imaging data will be performed for all endoscopies. To confirm eligibility at Visit 2, only the Visit 1 central reading will be made available to the site. In addition, at Visit 2, the Investigator will perform the NE to confirm the eligibility score and enter the result in the e-CRF. Thus, the participant will be considered eligible based on a Visit 1 central reading followed by a Visit 2 local reading NPS score of 5 or more and at least 2 on each side.

For the analysis of the primary endpoint, the central reading of Visit 2 will be used for comparison with the Week 24 reading. The sites will remove participant-identifying information from the imaging data header prior to sending the imaging data to the central reader.

Nasal endoscopy will be conducted at the Screening Visit (Visit 1), Visit 2, and Visits 4 to 9.

Further details on NE will be available in a separate operational manual provided to the sites.

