9.3.1 General considerations

The baseline value is defined generally as the last available value before first IMP administration.

The observation period will be divided into 2 segments:

- The **pre-treatment period** is defined as the period up to first IMP administration.
- The **treatment-emergent period** is defined as the period from the first IMP administration to the last visit in the study.

Dose regimen groups in the extension term after Week 24 will be defined as follows:

- 300 mg q2w group: participants who were administered at least 1 dose of the 300 mg q2w regimen and never experienced q4w administration during the extension term after Week 24
- 300 mg q4w group: participants who were administered at least 1 dose of the 300 mg q4w regimen during the extension term after Week 24

During the treatment term, including efficacy variable after Week 24, continuous variables and binary variables for efficacy by each visit will be summarized using descriptive statistics and frequency table in both the PP and mITT populations.

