## VERSION HISTORY

This statistical analysis plan (SAP) for study LPS16872 is based on the protocol version 1 dated 11-May-2021. There are no major changes to the statistical analysis features in this SAP compared to those in the protocol.

This SAP will be finalized before efficacy review.

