## **4.2 PARTICIPANT DISPOSITIONS**

The number (%) of participants included in each of the analysis populations listed in [Table 4](#) will be summarized.

Screened patients are defined as any patients who signed the informed consent.

Screen failures are defined as participants who consent to participate in the study but are not subsequently enrolled. The number (%) of screen failures and reasons for screen failures will be provided in the Screened population.

The number (%) of participants in the following categories will be provided:

- Screened participants
- Enrolled participants
- Enrolled but not exposed participants
- Enrolled and exposed participants
- Participants who completed the Week 24 study treatment period as per protocol
- Participants who did not complete the Week 24 study treatment period as per protocol and main reason for permanent treatment discontinuation including due to COVID-19
- Participants with nasal polyp score (NPS) improvement from baseline to both Weeks 16 and 24 is  $\geq 2$  points.
- 
- Participants who decreased treatment to the q4w regimen
  - Participants who completed the Week 52 study treatment period as per protocol
  - Participants who did not complete the Week 52 study treatment period as per protocol and the main reasons for permanent treatment discontinuation including due to COVID-19
  - Participants rescued prior to Week 52 by type of rescue
- Participants who continued the q2w regimen
  - Participants who completed the Week 52 study treatment period as per protocol

- Participants who did not complete the Week 52 study treatment period as per protocol and the main reasons for permanent treatment discontinuation including due to COVID-19
- Participants rescued prior to Week 52 by type of rescue

For all categories of participants (except for the screened categories), percentages will be calculated using the number of enrolled participants as the denominator.

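### The SAP adds a stable-disease condition to the q4w group, so a q4w-dosed participant who does not meet it appears in neither regimen column of the extension tables

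*SAP*

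**What the plan says.** Protocol section 9.3.1 defines the q4w group by treatment received: "participants who were administered at least 1 dose of the 300 mg q4w regimen during the extension term after Week 24". The SAP, under Dose regimen groups in section 4.1, narrows it to "participants with stable disease who were administered at least 1 dose of the 300 mg q4w regimen during the extension term after Week 24". In both documents the q2w group needs at least one q2w dose in the extension and is limited to participants who "never experienced q4w administration during the extension term after Week 24".

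The SAP uses the term stable disease without defining it. The definition is in the protocol, for example in footnote c to the schedule of activities: "Stable disease is defined as NPS improvement from baseline to both Weeks 16 and 24" of at least 2 points. SAP section 4.2 repeats the same threshold only as a disposition count ("Participants with nasal polyp score (NPS) improvement from baseline to both Weeks 16 and 24 is" at least 2 points). It does not label that count as stable disease or tie it to the regimen groups.

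The SAP version history states: "There are no major changes to the statistical analysis features in this SAP compared to those in the protocol". Appendix 2 of the SAP lists two changes from the protocol, to the treatment-emergent period and to the definition of rescue. The q4w group definition is not among them.

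**The concern.** Groups used as table columns should place every participant in exactly one column. The protocol's pair does this: a participant dosed in the extension either received q4w at some point or did not. The SAP's pair leaves a gap, because failing the stable-disease condition removes a participant from the q4w group while having had q4w bars entry to the q2w group.

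The regimen split matters in three sets of extension results: safety (SAP sections 4.1 and 4.7.2), Week 52 changes from baseline (4.5.2.2) and by-visit summaries after Week 24 (4.5.2.3). Each is planned by regimen with an overall column. An unclassified participant's adverse events and efficacy values would count in the overall column and in no regimen column. The q4w column could also disagree with SAP section 4.2, which counts participants who moved to q4w with no stable-disease condition attached.

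The condition may also select on outcome. It is a threshold on NPS improvement, and NPS is itself summarised at Week 52. Anyone it removes from the q4w column has, by definition, failed that threshold at Week 16 or Week 24.

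**Working it through.** The point rests on definitions rather than on a figure in the plan. The planned sample size only sets the scale, and it reproduces: P(X ≥ 10 | n = 20, p = 0.62) = 0.9077 against the stated 90%, and 20 / (1 − 0.20) = 25.

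**Step 1. Classify every participant dosed in the extension.**

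| Stable disease | Any q4w dose after Week 24 | Protocol 9.3.1 | SAP 4.1 |
|---|---|---|---|
| Yes | Yes | q4w | q4w |
| Yes | No | q2w | q2w |
| No | No | q2w | q2w |
| No | Yes | q4w | **no group** |

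The protocol assigns all four combinations. The SAP assigns three.

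**Step 2. Trace the fourth row through the populations.** SAP Table 4 puts no stable-disease or regimen condition on SAFE or PPE. The participant is in SAFE, and in PPE if no INCS was used during the study. The Week 52 responder proportion (SAP 4.5.2.1) is stated for PPE as a whole, so the participant counts there too. The loss is confined to the regimen columns.

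**Step 3. Ask how the fourth row could be filled.** There are two routes.

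- A participant is moved to q4w without meeting the criterion, which is a protocol deviation.
- The readings disagree. Protocol section 8.1.1 has every endoscopy read centrally, and the SAP analyses use the central score. Neither document says whether the local or the central NPS decides stable disease, at the time of the switch or when the groups are formed. A switch made on one reading could fail the criterion on the other.

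**Step 4. Illustrate the size.** Assume N participants in the extension, with N = 20 or 25 taken from the planned numbers, and k unclassified. The regimen columns sum to N − k while the overall column stays at N.

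| N | k = 1 | k = 2 | k = 3 |
|---|---|---|---|
| 20 | 19 (5% missing) | 18 (10%) | 17 (15%) |
| 25 | 24 (4%) | 23 (8%) | 22 (12%) |

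The documents give neither k nor the number expected to switch to q4w. The share of the q4w column that would be lost therefore cannot be stated.

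**The case against.** The strongest defence is that the added words describe the group and do not filter it. The protocol opens q4w only to participants with stable disease, and section 6.5 then says "However, any dose reduction is not allowed other than above". For anyone handled per protocol the two definitions give the same group, and the SAP's statement of no major changes fits a restatement. The reason for a regimen change is recorded in the e-CRF, so stable disease could be taken from the Investigator's determination, in which case no reading mismatch arises. This stands as a possible reading. It does not remove the gap for a participant switched in deviation, and the SAP does not say which reading it intends.

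The stakes are also limited. The SAP plans no hypothesis tests, the 52-week efficacy endpoints are exploratory, and the q4w group is selected on response by design, so it is not a fair comparator for q2w in any case. The two counts in SAP 4.2 would help expose a shortfall. All of this stands and keeps the point small.

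Three stronger readings are tempting, and the documents do not support them.

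- A reader might infer that the participant disappears from the extension tables. Population membership and the overall columns show otherwise.
- A reader might infer from the words "only the Visit 1 central reading will be made available to the site" that the Week 24 switch is judged on local scores. The sentence opens by limiting itself to confirming eligibility at Visit 2. It says nothing about release of Week 16 or Week 24 readings, and further endoscopy details are left to an operational manual that is not among the documents. What can be said is that the deciding reading is unspecified.
- A reader might put a percentage on the loss from the q4w column. That needs a number of switchers, which the documents do not give.

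**Conclusion.** The SAP departs from the protocol's q4w group definition without declaring it. Read literally, its two regimen groups do not cover everyone dosed in the extension. A q4w-dosed participant who does not meet the protocol's stable-disease criterion would be missing from both regimen columns for extension safety, Week 52 changes and by-visit summaries, while remaining in SAFE, in PPE if no INCS was used, and in the overall columns.

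How often this would happen cannot be known from the documents, and it may not happen at all. With about 25 participants enrolled, even one case would be visible. The exposure is limited to descriptive results by regimen. The Week 24 primary endpoint is unaffected.

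The correction is worth making because it costs almost nothing and changes nothing if the added words were only descriptive. If they act as a filter, it restores complete groups and prevents possible selection on NPS response in the q4w column.

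**What to change.** In SAP section 4.1, delete *with stable disease* from the q4w definition, so that groups follow the regimen actually received, as in protocol section 9.3.1. Add one line to the disposition summary giving the number of q4w participants who did not meet the stable-disease criterion on central reading.

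If the sponsor prefers to keep the condition, the SAP should define stable disease, name the reading that decides it, say in which column the remaining q4w participants are shown, and list the change in Appendix 2.

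The cost is three words removed and one count added, with no new data beyond the central readings already planned. The change concerns analysis grouping only and leaves the dosing rule as it is.

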## ***Rescue***

Participants who have undergone surgery or received SCS for any reasons are considered rescued. NP surgery and SCS use will be determined by the corresponding eCRF pages.

The date of rescue will be the earliest date of having undergone surgery or received SCS for any reason.

## **4.2 PARTICIPANT DISPOSITIONS**

The number (%) of participants included in each of the analysis populations listed in [Table 4](#) will be summarized.

Screened patients are defined as any patients who signed the informed consent.

Screen failures are defined as participants who consent to participate in the study but are not subsequently enrolled. The number (%) of screen failures and reasons for screen failures will be provided in the Screened population.

The number (%) of participants in the following categories will be provided:

- Screened participants
- Enrolled participants
- Enrolled but not exposed participants
- Enrolled and exposed participants
- Participants who completed the Week 24 study treatment period as per protocol
- Participants who did not complete the Week 24 study treatment period as per protocol and main reason for permanent treatment discontinuation including due to COVID-19
- Participants with nasal polyp score (NPS) improvement from baseline to both Weeks 16 and 24 is  $\geq 2$  points.
- 
- Participants who decreased treatment to the q4w regimen
  - Participants who completed the Week 52 study treatment period as per protocol
  - Participants who did not complete the Week 52 study treatment period as per protocol and the main reasons for permanent treatment discontinuation including due to COVID-19
  - Participants rescued prior to Week 52 by type of rescue
- Participants who continued the q2w regimen
  - Participants who completed the Week 52 study treatment period as per protocol

- Participants who did not complete the Week 52 study treatment period as per protocol and the main reasons for permanent treatment discontinuation including due to COVID-19
- Participants rescued prior to Week 52 by type of rescue

For all categories of participants (except for the screened categories), percentages will be calculated using the number of enrolled participants as the denominator.

### 4.3 PRIMARY ENDPOINT ANALYSIS

#### 4.3.1 Definition of endpoints

The primary endpoint is the proportion of responders, defined as the proportion of participants with a nasal polyp score (NPS) improvement from baseline  $\geq 1$ , at Week 24. Baseline will be the central reading at Visit 2. If a Visit 2 reading is missing, the central reading at Visit 1 will be used.

The NPS is assessed by central video recordings of nasal endoscopy (NE). The NPS is the sum of the right and left nostril scores and is graded based on polyp size as described below in Table 5.

**Table 5 - Endoscopic nasal polyp score**

Polyp Score	Polyp Size
0	No polyps
1	Small polyps in the middle meatus not reaching below the inferior border of the middle turbinate
2	Polyps reaching below the lower border of the middle turbinate
3	Large polyps reaching the lower border of the inferior turbinate or polyps medial to the middle turbinate
4	Large polyps causing complete obstruction of the inferior nasal cavity

Nasal endoscopy should be performed at the end of the scheduled visits before the administration of IMP and should be preceded by local administration of anesthetic drugs in combination with a decongestant. NE will be conducted at the Screening Visit (Visit 1), Visit 2, and Visits 4 to 9.

Standard video sequences will be downloaded or sent to a centralized reader. Centralized imaging data assessments and scoring by independent physician reviewer(s) for the imaging data will be performed for all endoscopies. To confirm eligibility at Visit 2, only the Visit 1 central reading will be made available to the site. In addition, at Visit 2, the Investigator will perform the NE to confirm the eligibility score and enter the result in the e-CRF. Thus, the participant will be considered eligible based on a Visit 1 central reading followed by a Visit 2 local reading NPS score of 5 or more and at least 2 on each side.

Further details on NE is available in a separate operational manual provided to the sites.

### 4.3.2 Main analytical approach

The number of participants and percentage with the 95% continuity corrected Wilson confidence interval (CI) will be provided at Week 24 using the PP population.

The main strategy for handling intercurrent events will be a Composite approach, where participants who are rescued (undergo surgery for NP or receive SCS for any reason) will be considered nonresponders for time points after rescue. Participants who have missing data at Week 24 will be considered nonresponders.

The date of rescue will be the earliest date of any intercurrent events that occur.

### 4.3.3 Sensitivity analysis

There are no sensitivity analyses planned.

### 4.3.4 Supplementary analyses

**The primary endpoint**, the proportion of responders, defined as the proportion of participants with a nasal polyp score (NPS) improvement from baseline  $\geq 1$ , at Week 24 will be analyzed using the mITT population and the following methodologies for intercurrent events:

- **Composite strategy:** Censor participants with INCS use, SCS, and surgery for CRSwNP prior to Week 24 at the earliest date of all intercurrent events. These participants will be categorized as nonresponders at timepoints after the censoring date.

Missing data related to the primary endpoint will be tabulated including by relation to the COVID-19 pandemic. If necessary, additional supplementary analyses will be presented.

### 4.3.5 Subgroup analyses

The number and percent of responders with NPS improvement from baseline  $\geq 1$  at Week 24 will be presented by the following subgroups within the PP analysis population:

- Age group (18-64, 65-74,  $\geq 75$  years)
- Gender (Male, Female).

Intercurrent events and missing data will be handled using the same methodology as Estimand 1. Participants who receive INCS are excluded from the PP analysis population. Participants who undergo surgery for NP, receive SCS for any reason, or have missing data will be considered nonresponders for time points after the earliest date of all intercurrent events that occur.

## 4.4 SECONDARY ENDPOINTS ANALYSIS

### 4.4.1 Key secondary endpoints

- Change from baseline to Week 24 in bilateral NPS

- Change from baseline to Week 24 in NC symptom severity score using the CRSwNP nasal symptom diary
- Change from baseline to Week 24 in opacification of sinuses assessed by CT scan using the LMK score

#### 4.4.1.1 Definition of endpoints

Change from baseline to Week 24 in bilateral NPS is defined as the difference between the central reading NPS at Week 24 and the central reading NPS at Visit 2. If the central reading value at Visit 2 is missing, the central reading value from Visit 1 will be used.

See Section 4.3.1 for additional details regarding NE.

